**Table 4 Dose adjustments for non-hematologic drug-related AEs, clinically significant in the opinion of the investigator**

Grade	Occurrence	Dose modification
1 or 2	Any time	No dose reduction.
3  (Persistent grade 2: Consider	1st and 2nd time	Hold selinexor and/or sorafenib. Resume selinexor and/or sorafenib at prior dose if recovery to $\leq$ Grade 1 or baseline occurs within 14 days. If toxicity persists for 15-28 days, hold therapy and resume at ONE dose level below current dose for selinexor OR sorafenib

similar dose adjustments if persistent and not responding to optimal management in the opinion of PI and treating physician)		OR both based on which medication is likely causing the toxicity ONLY after recovery of toxicity to $\leq$ Grade 2. Dose re-escalation to prior dose of selinexor OR sorafenib OR both is permitted if tolerated and no recurrent Grade 3 or 4 toxicities occur over 4 weeks while on the lower dose level.
	3 rd and 4th time	Hold selinexor and/or sorafenib. Follow until toxicity $\leq$ Grade 2. Resume at TWO dose level below current dose for selinexor OR sorafenib OR both based on which medication is likely causing the toxicity ONLY after recovery of toxicity to $\leq$ Grade 2. Dose re-escalation by one dose level every 4 weeks of selinexor OR sorafenib OR both is permitted if tolerated and no recurrent Grade 3 or 4 toxicities occur over the 4 weeks while on the lower dose level.
	5th time	Stop selinexor and sorafenib and discontinue patient. (For patients with clinical benefit/response from the combination we will consider continuation if toxicities resolve to $\leq$ grade 1 and with proper dose adjustments after consultation with the PI and the sponsor)
4	Any time	Stop selinexor and sorafenib and discontinue patient. (For patients with clinical benefit/response from the combination we will consider continuation if toxicities resolve to $\leq$ grade 1 and with proper dose adjustments after consultation with the PI and the sponsor)

- If the criteria to resume treatment are met, the subject should restart treatment at the next scheduled time point per protocol. However, if the treatment is delayed past the next scheduled time point per protocol, the next scheduled time point will be delayed until dosing resumes.

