Grade 4 (anorexia only)	See guidelines for Grade 2 anorexia.	Stop dosing of selinexor. Restart selinexor at 1 dose level reduction (Table 3) only if anorexia resolves to Grade $\leq$ 2, patient is clinically stable other contributing factors have been addressed.	
Nausea/ - acute (common)			
Grade 1	Insure adequate caloric intake and assess volume status. Consider alternate 5-HT3 antagonists and/or D2 antagonists as needed. Consider addition of NK1 antagonists. Consider addition of 4-8 mg dexamethasone or equivalent on the day after selinexor.	Maintain dose.	
Grade 2	See guidelines for Grade 1 nausea.  For additional options see NCCN guidelines for antiemesis c	Selinexor may be skipped intermittently while supportive medications are instituted, usually for <1 week.	

Toxicity and Intensity	Supportive treatment	Selinexor Dose Modification	
Grade 3	
See guidelines for Grade 1 nausea
 
For additional options see NCCN guidelines for antiemesisc
	
Interrupt selinexor dosing until resolved to Grade <math>\leq 2</math>, For first occurrence of Grade 3, if adequate supportive care resulted in nausea improving to Grade <math>\leq 1</math> within 3 days, restart selinexor at current dose.
 
Otherwise, restart selinexor at one dose level below (Table 3). If nausea stabilizes for at least 4 weeks at Grade <math>\leq 1</math>, then original dose of selinexor may be resumed.
	
Hyponatremia (common)			
Grade 1 (sodium levels $<$ Normal to 130 nM)	
Be certain sodium level is corrected for hyperglycemia (serum glucose <math>>150</math>mmol/L). Rule out other causes of low sodium (e.g., cardiac, hepatic, adrenal, renal and thyroid diseases, SIADH, Fanconi Syndrome, hyperglycemia, diuretic use).
 
Consider salt supplementation one – two times per day.
	Maintain dose.	

Toxicity and Intensity	Supportive treatment	Selinexor Dose Modification	
Grade 3 (sodium levels 126-129nM) without Symptoms	Be certain sodium level is corrected for hyperglycemia (serum glucose >150mmol/L). Rule out other causes of low sodium (e.g., cardiac, hepatic, adrenal, renal and thyroid diseases, SIADH, Fanconi Syndrome, hyperglycemia, diuretic use). Initiate salt supplementation two-three times per day.	Hold selinexor until Grade $\leq 1$ ( $\geq 130$ nM), restart on the same dose level.	

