Grade 3 (120-125 nM) or Grade 4 or any Grade 3 with Symptoms	Correct sodium as per institutional guideline Initiate salt supplementation two-three times per day.	Hold selinexor until resolved to Grade $\leq 1$ ( $\geq 130$ nM) then reduce selinexor dose by 1 level (Table 3). For Grade 3 hyponatremia, if serum sodium stabilizes to grade $\leq 1$ for at least 4 weeks, then original dose of selinexor may be resumed.	
Diarrhea (common)			
Grade 1+2	Diet recommendation as per guidelines (Benson, 2004) d . Institute standard anti-diarrheal therapy. After the first occurrence of diarrhea, loperamide 2 mg should be considered prophylactically approximately 1-2 hours before the administration of selinexor and repeated every 4 hours for the first 12 hours.	For Grade 2 only, reduce selinexor one dose level (Table 3) until resolved to $\leq$ Grade 1, then re-start at the current dose level.	

Toxicity and Intensity	Supportive treatment	Selinexor Dose Modification	
Grade 3	
Institute IV fluids                      Diet recommendation as per guidelines (Benson, 2004)d.
 
Institute standard anti-diarrheal therapy.
 
Once the symptoms resolve to <math>\leq</math>Grade 1, loperamide 2 mg should be considered prophylactically approximately 1-2 hours before the administration of selinexor and repeated every 4 hours for the first 12 hours.
	
Delay selinexor until resolved to <math>\leq</math> Grade 1, then reduce selinexor dose by one dose level (Table 3).
 
If diarrhea stabilizes for at least 4 weeks at Grade <math>\leq</math>1, then original dose of selinexor may be resumed.
	
Grade 4	
Rule out other causes of diarrhea, including infectious agents. In case of opportunistic infection, withdraw all steroids (with tapering if medically appropriate) until culture is negative. Follow institutional guidelines for Grade 4 diarrhea.
	
Delay selinexor until resolved to <math>\leq</math> Grade 1, then reduce selinexor dose by one dose level (Table 3).
	
Other selinexor-related adverse events*			
Grade 1 or 2	
Initiate standard supportive care and follow institutional guidelines.
	
Maintain dose.
	
Grade 3	
Initiate standard supportive care and follow institutional guidelines.
	
Delay dose until resolved to Grade <math>\leq</math> 1 or baseline, then reduce by one dose level (Table 3).
	

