Grade 4	
Initiate standard supportive care and follow institutional guidelines.
	
Delay dose until resolved to Grade <math>\leq</math>1 or baseline, then reduce by two dose levels (Table 3).
	

Toxicity and Intensity	Supportive treatment	Selinexor Dose Modification	
All dose modifications should be based on the worst preceding toxicity.			
* Isolated values of $\geq$ Grade 3 alkaline phosphatase values will NOT require dose interruption. Determination of liver vs. bone etiology should be made, and evaluation of gamma-glutamyl transferase (GGT), 5'-nucleotidase (5'NT), or other liver enzymes should be performed.			
a National Comprehensive Cancer Network® . NCCN Clinical Practice Guidelines in Oncology (NCCN Guidelines®): Fatigue. Available at http://www.nccn.org/professionals/physician_gls/pdf/fatigue.pdf			
b National Comprehensive Cancer Network® . NCCN Clinical Practice Guidelines in Oncology (NCCN Guidelines®): Palliative Care, version 1.2014. Fort Washington, NY. April 2014. Available at: http://www.lls.org/content/nationalcontent/resourcecenter/freeeducationmaterials/generalcancer/pdf/facts.pdf .			
c National Comprehensive Cancer Network® . NCCN Clinical Practice Guidelines in Oncology (NCCN Guidelines®): Antiemesis, version 2.2014. Fort Washington, NY. April 2014. Available at: http://www.nccn.org/professionals/physician_gls/PDF/antiemesis.pdf .			
d Benson AB, Ajani JA, Catalano RB, et al. Recommended guidelines for the treatment of cancer treatment-induced diarrhea. J Clin Onc 2004; 22:2918.			

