### 11.3 Statistical Analysis Plan

All patients who received any dose of the study agent will be included in the analysis for efficacy and safety. Demographic/clinical characteristics (including duration of response) and safety data of the patients will be summarized using descriptive statistics such as mean, standard deviation, median and range. For the primary efficacy analysis, we will estimate the ORR for the combination treatment, along with the 95% confidence interval. In addition, we will estimate composite CRc rate, partial response and marrow clearance rate within 3 months by FLT3 mutation. Patients who drop out of the study before completing all the cycles will be treated as “failures” for the primary analysis. ORR during the study period will also be presented with the 95% confidence interval. The association between ORR and patient’s clinical characteristics will be examined by Wilcoxon’s rank sum test or Fisher’s exact test, as appropriate. Toxicity type, severity and attribution will be summarized for each patient using frequency tables.

The distribution of time-to-event endpoints (DFS and OS) including overall survival and progression free survival will be estimated using the method of Kaplan and Meier. Comparisons of time-to-event endpoints by important subgroups will be made using the log-rank tests. Paired t-tests will be used to determine the immunological and molecular changes in the peripheral blood and bone marrow from baseline to the time of response, and to the time of disease progression.

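### Tables 4 and 5 of Section 5.2.2 give conflicting instructions for the same selinexor-related events and neither is given precedence; the grade 4 conflict can change who stops treatment

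*Combined protocol and SAP*

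**What the plan says.** Table 4 covers drug-related non-hematologic events that the investigator judges clinically significant, and it acts on selinexor, sorafenib or both.

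- Grade 1 or 2: "No dose reduction". A note in the table lets grade 2 be handled like grade 3 if it persists and does not respond to optimal management.
- Grade 3, first or second time: hold, then resume at the prior dose if recovery comes within 14 days.
- Grade 4, any time: "Stop selinexor and sorafenib and discontinue patient". An exception follows: "For patients with clinical benefit/response from the combination we will consider continuation if toxicities resolve to" grade 1 or lower, with dose adjustments and after consultation with the PI and sponsor.

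Table 5 in the same section (not the concomitant-medication table in Section 5.6.2, which has the same number) covers toxicities likely related to selinexor.

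- Grade 2 diarrhea: "For Grade 2 only, reduce selinexor one dose level (Table 3") until it resolves.
- Grade 3 anorexia, diarrhea and other events: resume one level lower after recovery.
- Grade 4 anorexia: "Restart selinexor at 1 dose level reduction (Table 3) only if anorexia resolves to Grade" 2 or lower. Grade 4 hyponatremia: "then reduce selinexor dose by 1 level (Table 3"). Grade 4 diarrhea: one level lower. Other grade 4 events: "then reduce by two dose levels (Table 3").

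Table 5 has no benefit condition for resuming, and its grade 4 rows require no consultation and say nothing about stopping sorafenib.

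On analysis, Section 11.3 states: "Patients who drop out of the study before completing all the cycles will be treated as" failures in the primary analysis.

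**The concern.** A grade 4 selinexor-related event in a patient with no benefit yet meets two instructions that cannot both be carried out: discontinue the patient, or resume selinexor at a lower level. This is first a safety matter. Section 9.3 also lists departures from the dose-reduction and discontinuation rules among its classes of deviation or violation, so an investigator who follows one table can be recorded as departing from the other.

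It may also reach the primary endpoint. Response is scored over the first three cycles. A patient taken off treatment in cycle 1 under one table could, under the other, stay on treatment and respond later in that window. Two investigators facing the same event could then generate different response data in a cohort of at most 20.

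**Working it through.** **1. Do the tables overlap?** Yes. Any non-hematologic event that is attributed to selinexor and judged clinically significant meets both definitions.

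**2. The rules side by side**

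| Event | Table 4 | Table 5 | What differs |
|---|---|---|---|
| Grade 4 anorexia, hyponatremia, diarrhea | Discontinue; continuation considered only with benefit and consultation | Selinexor resumed one level lower after recovery | Treatment status |
| Grade 4, other | Same | Selinexor resumed two levels lower after recovery | Treatment status |
| Grade 3 anorexia, diarrhea, other (1st or 2nd time, recovered within 14 days) | Prior dose | One level lower | Dose only |
| Grade 2 diarrhea, not persistent | No reduction | One level lower until resolved | Dose only |

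Grade 3 fatigue and nausea conflict only in part. Table 5 also keeps the current dose after a first episode, but only if it improves to grade 1 or lower within 7 days (fatigue) or 3 days (nausea), against 14 days in Table 4.

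**3. Size of the dose difference.** From Table 3, one level is 100 to 80 mg (80/100, a 20% cut) or 80 to 60 mg (60/80, a 25% cut). Two levels is 100 to 60 mg (a 40% cut) or 80 to 40 mg (a 50% cut). At grade 2 or 3 the tables therefore differ by 20% to 25% of each selinexor dose from those levels. At grade 4 they differ between a reduced dose and none.

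**4. Does Table 4's exception close the grade 4 gap?** Only for patients already benefiting. Section 7.2.5 places the first on-treatment marrow at day 28 (±7) of cycle 1. A patient with a grade 4 event before then will generally have no marrow response to invoke, yet could still respond within three cycles.

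**5. Does discontinuation mean failure?** Three passages bear on it.

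- Section 11.3 fails patients who drop out of the study before completing all the cycles. It defines neither term. The cycles could be the three of the response window or the 24 planned in Section 5.3.1.
- Section 8.8 scores a patient who stops before three cycles on the best response up to time off study. A CRc reached before stopping would count.
- Section 9.1.4 keeps patients who stop treatment on study for follow-up. On that reading they have not dropped out.

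The same patient can be a failure, or be scored on what was observed, depending on which passage is applied.

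**6. Can an effect size be computed?** The plan's own figures were reproduced first. The inputs are the looks at 5, 10 and 15 patients, the boundaries in Tables 6, 7, 9 and 10, and independence of response and toxicity:

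P(stop early) = 1 − P(no futility stop) × P(no toxicity stop)

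- FLT3-inhibitor-naive cohort, CRc 35%, toxicity 30%: 1 − 0.8319 × 0.9156 = 0.238 (Table 8: 0.2384).
- FLT3-inhibitor-failure cohort, CRc 20%, toxicity 30%: 1 − 0.8926 × 0.8043 = 0.282 (Table 11: 0.2820).

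These figures take the true rates as given and do not depend on either dose table. The conflict could enter only by lowering the true CRc rate. To show the direction, let q be the share of would-be responders lost because grade 4 leads to discontinuation and is scored as failure. This q is an assumption; nothing in the documents supplies it. The CRc rate becomes the target × (1 − q), with toxicity held at 30%.

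| q | Naive: CRc, P(stop) | Failure: CRc, P(stop) |
|---|---|---|
| 0 | 35.0%, 0.238 | 20.0%, 0.282 |
| 5% | 33.25%, 0.264 | 19.0%, 0.294 |
| 10% | 31.5%, 0.294 | 18.0%, 0.306 |
| 20% | 28.0%, 0.363 | 16.0%, 0.336 |

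This shows how the design would respond. It does not estimate the effect of the conflict.

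**The case against.** The strongest reply is that the protocol's structure settles the matter. The text between the tables describes the preceding rules as general and as guidance to the investigator. It then introduces Table 5, whose title calls its guidelines specific, for selinexor toxicities. Specific over general is a natural reading, and Table 5 could be supplying the dose adjustments that Table 4's exception leaves open. Section 5.2.4 allows further reductions and other modifications after discussion, and Section 9.1.3 lists no grade 4 trigger for mandatory discontinuation. All of this is fair, and it makes calling the tables flat opposites too strong. But no sentence gives Table 5 precedence, and the discretion clauses permit departures without setting a default. For a patient with no benefit yet, Table 4's exception does not apply.

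Two stronger readings are tempting, and the documents do not support them.

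- A reader might infer that a patient discontinued under Table 4 is automatically a failure. Sections 8.8 and 9.1.4 do not allow that as a general statement. The grade 2 and 3 conflicts do not bear on it at all, since neither table takes those patients off treatment at that point.
- A reader might infer from Section 2.2.2 that the conflict will be frequent, since it reports diarrhea in 82% and grade 3/4 fatigue in 18% of AML patients on selinexor. The 82% pools grades 1 and 2. The 18% pools grades 3 and 4 of a toxicity for which Table 5 has no grade 4 row. Neither gives a rate for the grade 4 conflict.

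**Conclusion.** The point holds as an internal inconsistency. Tables 4 and 5 cannot both be followed for a grade 4 selinexor-related event in a patient without benefit. They also prescribe different doses for grade 3 anorexia, diarrhea and other events that recover within 14 days, and for non-persistent grade 2 diarrhea. The grade 4 conflict is safety-relevant and can change who stops treatment. Its effect on the primary endpoint is conditional on how drop-out is read, and the documents give neither a grade 4 rate nor the share of such patients who would have responded, so no effect size can be stated. One reclassified patient is 1/20, or 5 percentage points, in a full cohort, but that is true of any patient. The plan's stated operating characteristics stand as published. No view is taken on which dose rule is right.

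**What to change.** The investigator and sponsor should:

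1. reconcile Tables 4 and 5 for grades 2, 3 and 4, including what happens to sorafenib and whether benefit and consultation are conditions for resuming selinexor after grade 4;
2. state in Section 5.2.2 which table governs a selinexor-related event;
3. state in Section 11.3 whether stopping treatment for toxicity counts as dropping out and what completing all the cycles means, in terms consistent with Sections 8.8 and 9.1.4.

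The choice of clinical rule is theirs. The cost is amendment wording: the sample size, the stopping boundaries and Tables 8 and 11 need no change.

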### 5.2.3 Intra-patient dose escalation

Intra-patient dose escalation of selinexor and sorafenib (in accordance with the dosing schema in table 3) will be permitted provided:

- Patient has completed  $\geq 1$  cycle at their current dose level
- Patient has not experienced any grade 3 or higher non-hematologic drug-related toxicity, and
- Patient has not experienced hematologic DLT, and
- At least 3 patients have been treated at the next higher dose level and followed for at least 28 days without experiencing DLT.
- The dose may be escalated by one dose level per cycle (per table 3) provided such dose level does not exceed RP2D.
- Dose escalation of only one of the two agents is allowed if judged in the best interest of the patient (e.g., in patients with anorexia this would be likely secondary to selinexor, in patients with skin rash this would be likely secondary to sorafenib). However, the dose of any agent cannot be escalated beyond the established RP2D for that agent.

**5.2.4 Modifications of dose schedules other than the above** will be allowed within the following guidelines:

- 5.2.4.1 Further dose reductions can be made to keep clinically significant toxicities grade  $\leq 2$ .
- 5.2.4.2 Dose adjustments by more than 1 dose level at a time (e.g., from selinexor 80 mg twice weekly to 40 mg twice weekly) can be considered when judged in the best interest of the patient (e.g. severe myelosuppression) when toxicity has resolved. The reason for this reduction will be discussed with the PI or Co-PI and documented in the medical record.
- 5.2.4.3 A patient who has had a dose reduction because of any of the reasons mentioned above may have their dose escalated provided the patient has remained free of toxicity requiring dose adjustments as defined above for at least 1 month. Escalation will be made by 1 dose-level increment only, and not more frequent than every month.
- 5.2.4.4 Treatment interruptions and dose modifications other than the ones mentioned above can be considered after discussion with the PI, sponsor and proper documentation of the rationale. Dose adjustment/delay of only one of the agents is permissible if the toxicity is most likely judged to be related to one of the agents by the investigator (e.g., in patients with anorexia this would be likely secondary to selinexor, in patients with skin rash this would be likely secondary to sorafenib).

**5.3 Duration of Therapy**

In the absence of treatment delays due to adverse events, treatment may continue until one of the following criteria applies:

1. Clinically significant progressive disease, or
2. Intercurrent illness that prevents further administration of treatment, or
3. Patient request, or
4. General or specific changes in the patient's condition render the patient unacceptable for further treatment in the judgment of the investigator, or
5. Unacceptable toxicity that in the opinion of the investigator makes it unsafe to continue therapy.

- 5.3.1 It is planned that up to a total of 24 cycles of therapy will be administered for patients deriving benefit from this regimen.

Continuation of therapy for patients completing 24 cycles of therapy may be considered on a case-by-case basis after discussion with the principal investigator.

- 5.3.2. All patients receiving at least one dose of any of the two drugs will be considered evaluable for toxicity.

## 5.4 Drug administration

### (A) Selinexor administration

#### 5.4.1 Dosage form

Selinexor tablets are manufactured by KABS Laboratories (Montreal, ON) for Karyopharm, Therapeutics (Newton, MA) using methods in accordance with Food and Drug Administration (FDA) guidelines for the manufacture and testing of antineoplastic agents for human use. The tablets are prepared from a common blend of excipients and all tablet excipients are GRAS (generally regarded as safe) listed and suitable for use in pharmaceuticals. Selinexor is an investigational agent supplied to investigators of this study by Karyopharm Therapeutics at no cost.

Selinexor will be supplied as clear-coated white to off-white tablets for oral administration in two (2) dose strengths: 10 and 25 mg of active ingredient per tablet, with transition to the 20 mg tablets as these supplies become available. The tablets are distinguishable by size and debossing (K10 and K25 respectively). Bulk bottles of 50 tablets per bottle will be supplied for each of the two strengths. The 20 mg tablets will be supplied in blister packs. Tablets of selinexor should not be crushed because of increased risk of dermatologic toxicity if powder comes in contact with skin.

